10.2.5 Exploratory Analysis

The success of LLA will be determined by the cold test results (+/-) and the number of supplemental injections. The onset of LLA will be determined by the duration until adequate lip numbness and the duration until negative cold response after IANB.

For the exploratory objective we will compare the success and onset of LA in the two study arms. For comparison of success of LLA between the 2 arms we will use Fisher's exact test. For comparison of onset of LLA between the 2 arms we will use a Wilcoxon Rank Sum test.

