Although adequate lip numbness is achieved, pulpal anesthesia at the same time is not always guaranteed for symptomatic teeth (17). Therefore, pulpal anesthesia will be tested with cold test, after a wait time of 10 minutes, after obtaining adequate lip numbness with (Endo-Ice, Coltene, USA) in the proposed study in an

CONFIDENTIAL

attempt to test/confirm pulpal anesthesia. This is a routine procedure for the confirmation of pulpal anesthesia. This will be done to determine the success of IANB with either Lidocaine or Bupivacaine. All other injections, if needed, apart from the IANB, will be administered with Lidocaine only in both groups.

A supplemental buccal infiltration and intraligamentary (IL) injection will be given with Lidocaine HCl 2% 1:100000 to all patients, irrespective of their grouping. This approach is a routine and highly recommended for symptomatic teeth (24, 25). The effect of pulpal anesthesia will be tested with cold test (Endo-Ice, Coltene, USA). The algorithmic chart for anesthetic administration in Fig 1. will be followed as the guideline. Additional supplemental injections will be administered as portrayed in the chart, with Lidocaine HCl 2% 1:100000 if needed in order to obtain complete pulpal anesthesia.

Subjects who need supplemental injections more than 2 times will be excluded from the study because number of injections may also contribute to postoperative pain and discomfort.

The maximum recommended dose for lidocaine is 500mg per day, and it shouldn't exceed 7mg/kg of body weight. The maximum recommended dose for bupivacaine is 400 mg per day. There are no reported risks with these doses. All these supplemental injections will be performed with Lidocaine HCl 2% 1:100000 in both groups.

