5.1 Inclusion Criteria

In order to be eligible to participate in this study, an individual must meet all of the following criteria:

1. Patients between the ages of 18-85 years old.
2. Patients with pulpal diagnosis of either symptomatic irreversible pulpitis or pulp necrosis and periapical diagnosis of normal apical tissues, symptomatic apical periodontitis or asymptomatic apical periodontitis.
3. Patients who only have one tooth with odontogenic pain at the time point of the screening.
4. Patients who are treatment planned, and have agreed to have, pulpectomy/endodontic debridement.
5. Patients with acute dental pain of at least 3/10 on NRS.
6. Patients must be able to comprehend and complete all study questionnaires.
7. Patients must be able to comprehend the description of the study protocol and written consent.
8. Patients must be available to be contacted by text messages, phone calls or email during 5 days after the pulpectomy/endodontic debridement.

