6.1.7 Starting Dose and Dose Escalation Schedule

The initial dose administered for groups will be one cartridge (1.8 mL for Bupivacaine, 1.7 mL for Lidocaine).

If adequate anesthesia is not achieved within 15 minutes determined by the treating dentist by;

1. Asking the subject for reporting of lip numbness

CONFIDENTIAL

2. Testing and comparing with the contralateral side of the lip with a blunt instrument such as mirror handle, a second injection of the same dosage of the same drug will be provided.

If the IANB fails to provide adequate lip numbness after the second injection after a wait time of a further 15 minutes (total wait time 30 minutes), the subject will discontinue with the study agent/control agent, will be excluded from the study and the treating dentist will be unblinded and routine protocol will be followed; Lidocaine 2% with 1:100,000 epinephrine will be administered either with an IANB, infiltration or intraosseous anesthesia as decided by the treating dentist.

[figure not shown]
Whether the adequate lip numbness is gained either after the 1st or 2nd IANB, another 10 minutes will be waited to achieve pulpal anesthesia;

1. Cold Test - As per standard of care, Endo-Ice (Coltene, USA) will be administered to subjects to determine the success of pulpal anesthesia. This is a routine step in endodontic treatment. A cotton pellet is sprayed with the refrigerant spray and applied the tooth. A painful response will indicate inadequate pulpal anesthesia.

Subjects in each group will also receive a buccal infiltration and IL injection with Lidocaine which is highly recommended for symptomatic teeth. The Cold Test will be repeated to determine anesthesia. The algorithmic chart for anesthetic administration in Fig. 1 will be followed as the guideline. Additional supplemental injections will be administered as portrayed in the chart with Lidocaine HCl 2% 1:100,00 in both groups if needed, until pulpal anesthesia is obtained to initiate treatment or to continue with the treatment, without jeopardizing the maximum dose limit for the subject.

Subjects who need supplemental injections more than 2 times will be excluded from the study

Figure 1: Algorithm to Follow Adequate Soft Tissue and Pulpal Anesthesia

CONFIDENTIAL

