10.2 Statistical Analysis

10.2.1 Analysis Dataset

The analysis dataset for study and control group will include subjects who receive IANB either with the study agent Bupivacaine or the control agent Lidocaine for the pulpectomy/endodontic debridement of symptomatic mandibular molar teeth diagnosed with either symptomatic irreversible pulpitis or pulp necrosis and periapical diagnosis of normal periapical tissues, asymptomatic or symptomatic apical periodontitis. The dataset will consist of preoperative data (demographics, preoperative pain assessment, PCS, LOT-R), initial clinical examination (cold test, percussion hypersensitivity), diagnosis, intraoperative data, initial and follow up OHIP-14 scores and postoperative pain, medication use and numbness. All analyses will be intent-to-treat dataset that includes all randomized patients and will use the analysis dataset.

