10.2.2 Descriptive Statistics

Within each randomized treatment group appropriate descriptive statistics including means and standard deviations for quantitative variables and frequency and percentages for categorical variables will be calculated. Wilcoxon Rank Sum test and Fisher's exact test will be used to compare the two intervention groups with respect to the following baseline variables:

- Demographics (age, sex, race, ethnicity)
- Initial pain intensity and duration
- Pain medication use
- Pain Catastrophizing Scale
- Initial diagnosis (symptomatic irreversible pulpitis with/without symptomatic apical periodontitis and pulp necrosis with symptomatic apical periodontitis)
- Initial clinical testing of cold response (positive/negative)
- Initial clinical testing of percussion hypersensitivity (painful/not painful)

Any variable deemed significant will be controlled for in the primary, secondary and exploratory analyses. All analyses will be done with significance level of 5% (2-sided) unless specified otherwise.

CONFIDENTIAL

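### Section 10.2.5 compares cold-test success without regard to preoperative cold response, so teeth already cold-negative before injection can dilute this exploratory between-arm difference

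*Combined protocol and SAP*

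**What the plan says.** Section 5.1 admits "Patients with pulpal diagnosis of either symptomatic irreversible pulpitis or pulp necrosis", and neither 5.1 nor 5.2 requires a positive cold response. Section 10.2.2 lists the initial cold response, scored positive or negative, among the baseline variables to be tabulated and tested between arms.

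After the block, section 2.2.2 says that "pulpal anesthesia will be tested with cold test, after a wait time of 10 minutes", counted from adequate lip numbness, and gives the purpose: "This will be done to determine the success of IANB with either Lidocaine or Bupivacaine". Section 6.1.7 gives the scoring rule: "A painful response will indicate inadequate pulpal anesthesia". Every subject then receives lidocaine by buccal infiltration and intraligamentary injection, and the cold test is repeated.

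Section 10.2.5 defines the analysis: "The success of LLA will be determined by the cold test results (+/-) and the number of supplemental injections". Success is compared by Fisher's exact test and onset, which includes time to a negative cold response, by the Wilcoxon rank sum test. Baseline cold response is not mentioned there.

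Two other provisions matter. Section 10.2.1 states that "All analyses will be intent-to-treat dataset that includes all randomized patients". Section 10.2.2 provides the only route to adjustment: "Any variable deemed significant will be controlled for in the primary, secondary and exploratory analyses".

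**The concern.** A tooth that did not respond to cold before any drug was given cannot be expected to give a painful response afterwards. Under the 6.1.7 rule it scores as adequately anesthetised in either arm, and so says nothing about the difference between the drugs.

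The direction matters because the exploratory objective (3.3) asks whether bupivacaine is no different from lidocaine in pulpal anesthesia success and onset. Uninformative successes pull the comparison toward that answer. The protocol itself gives the disputed pulpal success of bupivacaine as its reason for collecting these data (2.3 and 3). A finding of little difference would be hard to read if part of it came from teeth that could not show one.

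The adjustment rule in 10.2.2 does not solve this. It is triggered by a significant imbalance between arms, whereas dilution occurs when cold-negative teeth are perfectly balanced. The Fisher test named in 10.2.5 also takes no covariate.

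**Working it through.** **The plan's own figures.** The documents give no power or effect size for the cold-test comparison. The only sample-size statement is for the primary endpoint (10.1): 40 per arm, difference 9.3, SD 13.3, two-sided 2.5%. A noncentral t calculation with 78 degrees of freedom gives 79.8% power against the stated 80%, and 80/0.8 = 100 enrolled. I therefore use 50 per arm (enrolled) and 40 per arm (expected after dropout).

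**Assumptions.** These are the cold-negative share f among teeth reaching the test, equal in both arms, and the success rates p1 and p2 in cold-positive teeth. None is in the documents. Teeth that are cold-negative at baseline are assumed to stay so.

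**Dilution among tested teeth**

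- Observed success in arm i = f + (1 − f)·pi.
- Risk difference = (1 − f)(p2 − p1).
- Failure rate in arm i = (1 − f)(1 − pi), so the ratio of failure rates is (1 − p2)/(1 − p1), free of f.

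For a true difference of 30 points:

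- f = 10%: 0.9 × 30 = 27 points
- f = 20%: 0.8 × 30 = 24 points
- f = 40%: 0.6 × 30 = 18 points

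Worked example, 40% against 70% with f = 20%:

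- Observed rates: 0.2 + 0.8 × 0.4 = 52% and 0.2 + 0.8 × 0.7 = 76%.
- Odds ratio: (0.76/0.24)/(0.52/0.48) = 2.92, against (0.70/0.30)/(0.40/0.60) = 3.50 undiluted.
- Ratio of failure rates: 0.24/0.48 = 0.50, against 0.30/0.60 = 0.50. It is unchanged.

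**Confidence interval, same example, 50 per arm.** Half-width = 1.96·√[(p1q1 + p2q2)/n], where q = 1 − p.

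- All teeth: 1.96·√[(0.2496 + 0.1824)/50] = 0.182, so 24 ± 18 points.
- Cold-positive only, n = 50 × 0.8 = 40: 1.96·√[(0.24 + 0.21)/40] = 0.208, so 30 ± 21 points.

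**Power.** Exact enumeration of the two-sided 5% Fisher test, all N per arm against N(1 − f) per arm:

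| Assumed rates | N | f | All teeth | Cold-positive only |
|---|---|---|---|---|
| 10% vs 30% | 50 | 20% | 31.1% | 53.4% |
| 40% vs 70% | 50 | 20% | 64.2% | 72.5% |
| 65% vs 85% | 50 | 10% | 50.0% | 50.2% |
| 70% vs 85% | 50 | 10% | 30.6% | 30.4% |
| 20% vs 50% | 40 | 40% | 30.1% | 49.3% |
| 80% vs 95% | 40 | 20% | 27.8% | 27.6% |

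Restriction gains about 20 points of power in some scenarios and nothing in others. These are examples, not bounds.

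**If lip-numbness failures count as failures.** Subjects without lip numbness after two blocks leave before any cold test (5.3, 6.1.7). Let L1 and L2 be the lip-numbness success rates, taken as the same for cold-positive and cold-negative teeth. The all-teeth difference becomes f(L2 − L1) + (1 − f)(L2p2 − L1p1). The first term vanishes only if L1 = L2; otherwise the factor is not exactly (1 − f).

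**The case against.** The strongest reply is that 10.2.5 does not name its analysis set. Section 10.2.1 refers to all randomized patients, and 5.8.2 says that block and supplemental failures will be analysed later for a difference in success between the drugs. If lip-numbness failures are scored as failures, a cold-negative tooth can fail, and at a rate that depends on the drug. This stands, and it limits the exact factor to teeth that reach the test.

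A reader might also infer that cold-negative teeth cannot fail the plan's success measure at all. The documents do not support that. Success also involves the number of supplemental injections, and 10.1.2 links supplements to pain while the tooth is being worked on. However, 4.1.3 lists the cold test and the number of supplemental injections as separate endpoints, so the cold-test comparison can still be diluted. Any dilution of the injection count is not quantified here.

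Figure 1 and the supplementary method form govern the testing sequence and are not shown. Either might already separate these teeth, so the point is conditional on their content.

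Finally, comparing success in the whole enrolled population is a legitimate question, and 10.2.2 will already tabulate baseline cold response by arm. Both are true. Neither gives an estimate in the teeth where the cold test can distinguish the drugs.

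**Conclusion.** The point holds as a low-cost improvement to one exploratory comparison. As written, 10.2.5 lets teeth that were cold-negative before injection count as cold-test successes under either drug, unless material not shown says otherwise. Among tested teeth the risk difference shrinks by the factor (1 − f) and the odds ratio moves toward 1, while the ratio of failure rates is unaffected. The size rests on f and on success rates that the documents do not give; if few teeth are cold-negative, the effect is small.

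Two stronger readings should be resisted. A reader might infer that restriction will increase power. It may, but some assumed rates show no gain, and the interval is usually wider. A reader might also infer that the main result or the stopping rule is compromised. The primary endpoint is OHIP-14 change and the secondary endpoints are pain, medication use and numbness, none of which is scored by the cold test. The rule in 10.2.6 counts intraoperative exclusions for lip numbness or repeated supplementation, and nothing is claimed about it here.

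**What to change.** In 10.2.5:

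1. Define cold-test success of the nerve block as the result of the first cold test after the block, the test that 2.2.2 assigns to that purpose. Analyse it in teeth that were cold-positive at the preoperative examination, and give the between-arm difference with a 95% confidence interval.
2. State how subjects excluded for lack of lip numbness (5.3, 5.8.2) are counted, given the all-randomized statement in 10.2.1.
3. Report the number of cold-negative teeth per arm and show the all-teeth comparison alongside.
4. Report time to negative cold response and number of supplemental injections by baseline cold response. Onset should not rest on the first cold test alone: that test falls a fixed 10 minutes after lip numbness and would only repeat the lip-numbness time plus 10 minutes.
5. If Figure 1 or the supplementary method form already separates cold-negative or necrotic teeth, cite it.

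The cost is wording. Baseline cold response is already in the dataset (10.2.1, 10.2.2), and restricting on a finding made before injection keeps the randomized comparison within the retained teeth. The intraoperative form is not in the documents, so confirm that it records the first cold result separately from later ones. The price is fewer teeth in the restricted analysis and usually a wider interval.

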2.2.1 Clinical Data to Date

Bupivacaine stabilizes the neuronal membrane and prevents the initiation and transmission of nerve impulses, thereby effecting LA. The onset of action following dental injections is usually 2 to 10 minutes and anesthesia may last two or three times longer than lidocaine and mepivacaine in dental use, for many patients up to 7 hours. The duration of anesthetic effect is further prolonged by the addition of epinephrine 1:200,000. After injection of bupivacaine for peripheral nerve block in man, peak levels of bupivacaine in the blood are reached in 30 to 45 minutes, followed by a decline to insignificant levels during the next three to six hours. It has also been noted that there is a period of analgesia that persists after the return of some sensation, during which time the need for strong analgesic is reduced. Because of its amide structure, bupivacaine is not detoxified by plasma esterases but is detoxified via conjugation with glucuronic acid, in the liver. When administered in recommended doses and concentrations, bupivacaine does not ordinarily produce irritation or tissue damage, and does not cause methemoglobinemia.

CONFIDENTIAL

This material is the property of the NYU School of Medicine and Langone Medical Center. Do not disclose or use except as authorized in writing by the study sponsor

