4.1.3 Exploratory Endpoints

- Cold test results (+/-)
- Number of supplemental injections
- Duration until adequate lip numbness is obtained (in minutes)
- Duration until negative cold response is obtained (in minutes)

CONFIDENTIAL

This material is the property of the NYU School of Medicine and Langone Medical Center. Do not disclose or use except as authorized in writing by the study sponsor

5 Study Enrollment and Withdrawal.

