After the adequate lip numbness is gained, another 10 minutes will be waited to achieve pulpal anesthesia; Cold Test – As per standard of care, Endo-Ice (Coltene, USA) will be administered to subjects to determine the success of pulpal This is a routine step in endodontic treatment. A cotton pellet is sprayed with the refrigerant spray and applied the tooth. A painful response will indicate inadequate pulpal anesthesia.

Subjects in each group will also receive a buccal infiltration and IL injection with Lidocaine which is highly recommended for symptomatic teeth. The Cold Test will be repeated to determine anesthesia. The algorithmic chart for anesthetic administration in the supplementary form *Pulpectomy/Endodontic Debridement Method* will be followed as the guideline. Additional supplemental injections will be administered as portrayed in the chart with Lidocaine HCl 2% 1:100,00 in both groups if needed, until pulpal anesthesia is obtained to initiate treatment, without jeopardizing the maximum dose limit for the subject.

Subjects who need supplemental injections more than 2 times will be excluded the study.

4. Intra- and Immediate Post-operative Data Collection:

- Pre-operative data obtained after clinical and radiographic examination which are performed as standard of care, before the treatment procedure, such as cold test response, percussion hypersensitivity, pulpal and periapical diagnosis will be collected by a study investigator by the end of the treatment, together with the intraoperative and immediate postoperative data.
- Intraoperative data such as number of cartridges used, time for adequate anesthesia, additional supplementary anesthesia will be collected.
- Intraoperative pain will be evaluated on a NRS by asking the subject directly after treatment.

5. Remote Data Collection:

Subjects will receive surveys remotely either by e-mail through REDCap, which will ask about their pain intensity reported on an NRS, analgesic medication use and numbness. REDCap surveys will be sent at 6, 12, 24, 48, 72, 96 and 120 hours after treatment. On day 1 and 5, subjects will be assessed by OHIP14.

If subjects do not have access to the Internet, a study team member will call them. Paper questionnaires will also be an option if no other methods are convenient for subjects. If they prefer to fill in the questions and questionnaire on paper, they will be asked to bring them to their second appointment.

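### Time to a negative cold response does not measure pulpal onset of the randomized block: it is lip-numbness time plus 10 minutes, or a time reached after lidocaine given to both arms

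*Combined protocol and SAP*

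**What the plan says.** Section 4.1.3 lists the time to a negative cold response, in minutes, as one of four exploratory endpoints. Section 10.2.5 makes it one of two onset measures: "The onset of LLA will be determined by the duration until adequate lip numbness and the duration until negative cold response after IANB". The arms are compared with a Wilcoxon rank-sum test, at the two-sided 5% level that Section 10.2.2 sets by default.

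Three places describe when the cold test is done, and they agree:

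- Section 2.2.2: "pulpal anesthesia will be tested with cold test, after a wait time of 10 minutes, after obtaining adequate lip numbness".
- Section 6.1.7: "Whether the adequate lip numbness is gained either after the 1st or 2nd IANB, another 10 minutes will be waited to achieve pulpal anesthesia".
- Section 7.1.1: "After the adequate lip numbness is gained, another 10 minutes will be waited to achieve pulpal anesthesia".

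Sections 6.1.7 and 7.1.1 then go on: "Subjects in each group will also receive a buccal infiltration and IL injection with Lidocaine". After that the cold test is repeated. Section 2.2.2 confirms that this supplement goes to everyone regardless of arm, and that every injection other than the IANB is lidocaine. It also says that the first cold test is there to judge whether the IANB succeeded.

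Two further facts matter. Section 2.2.1 says of bupivacaine: "The onset of action following dental injections is usually 2 to 10 minutes". Section 5.1 admits teeth with pulp necrosis, and Section 10.2.2 records the baseline cold response as positive or negative.

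**The concern.** An onset time needs observations close enough together to show when the effect began, and nothing given in between that could produce the same effect. The described schedule has neither. There is no cold test before the end of the 10-minute wait, and the next one follows an active anesthetic given to both arms.

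Sections 2.3 and 3 give the unsettled literature on bupivacaine's success and onset as the reason for collecting these data. If the endpoint is analyzed as written, a statement about pulpal onset could be wrong in either direction: a real difference could go unseen, or more frequent block failure in one arm could be reported as slower onset.

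**Working it through.** **Plan's own figure.** The documents give no figure for this endpoint. The only sample-size calculation (Section 10.1) is for OHIP-14: 40 per arm, difference 9.3, SD 13.3, two-sided 2.5%. It reproduces: noncentral-t power is 79.8%, and the difference detectable at 80% power is 9.32. It is used below only for the 40 per arm.

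**Step 1: which values can be recorded.** Let L be the time to lip numbness, P the true time to pulpal anesthesia from the IANB, and D the recorded time to a negative cold response. The first test is at L + 10.

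- First test negative (P no later than L + 10): D = L + 10.
- First test positive: D = L + 10 + s, where s is the further time until a repeat test is negative. That test follows lidocaine in both arms.

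P appears in neither expression. It only decides which line applies. For example, with lip numbness at 6 minutes, pulpal onset anywhere from 6 to 16 minutes is recorded as 6 + 10 = 16. D can never be below 10 minutes. The usual onset range in Section 2.2.1 (not stated to be pulpal) is 2 to 10 minutes, so it lies at or before the earliest possible test.

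**Step 2: effect on the rank test.** Adding 10 to every value leaves the ranks unchanged. If all first tests are negative, the Wilcoxon p-value for D is identical to that for L. If some are positive, those patients move up in rank by s, so the pooled test reflects L together with the frequency of first-test failure. It cannot separate a late block from a failed one, because lidocaine intervenes.

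**Step 3: illustration.** These assumptions are not in the documents: L is gamma with shape 4 and scale 1.5 (mean 4 × 1.5 = 6 minutes) in both arms unless shifted; pulpal onset is uniform within the 10-minute wait; the repeat test is 5 minutes later and negative. There are 40 per arm, a two-sided 5% test and 2,000 simulated trials. Entries are the share of trials with p < 0.05.

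| Scenario | True pulpal onset, if observed | Recorded D | Lip-numbness time |
|---|---|---|---|
| No difference | 4.7% | 5.0% | 5.0% |
| Pulpal onset shifted 2 min, all first tests negative | 62% | 6.0% | 6.0% |
| Pulpal onset shifted 4 min, all first tests negative | over 99% | 4.5% | 4.5% |
| Lip numbness shifted 2 min, all first tests negative | 52% | 88% | 88% |
| First-test failure 30% vs 60%, same onset where the block works | 4.9% | 44% | 4.6% |

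The simulation error is √(0.05 × 0.95 / 2,000) = 0.5 points near 5%, and √(0.44 × 0.56 / 2,000) = 1.1 points at 44%. The 6.0% and 4.5% entries are therefore the nominal level within error. In rows 1 to 4 the p-values for D and for lip numbness agreed in every simulated trial.

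**Step 4: teeth already cold-negative.** A necrotic tooth may not respond to cold before any injection. If it is then negative at the first test, D = L + 10 whatever the block has done. The plan gives no rule for such teeth, nor for patients who never become negative and leave under Section 5.3.

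**The case against.** The strongest reply is that the governing algorithm is Figure 1, together with a supplementary method form, and neither is in the text supplied. Either could include a retest before lidocaine. That limits the point to the visible text. Even so, three sections describe the sequence, none mentions such a retest, and all patients are said to receive the lidocaine.

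It is also fair that this is one exploratory endpoint. The stopping rule in Section 10.2.6 uses intraoperative exclusions, not cold-response times.

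Three stronger readings are tempting but not supported:

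- A reader might infer that the schedule guarantees a result of no difference. It does not. A difference in lip-numbness time carries through in full, and unequal block failure shifts the pooled times, as the last two rows of the table show.
- A reader might infer that block success will be scored after lidocaine, which would pull the arms together. Section 2.2.2 assigns that role to the first cold test. What remains is that Sections 4.1.3 and 10.2.5 do not repeat it, and that 10.2.5 also counts supplemental injections toward success.
- A reader might infer that lip numbness is checked only at 15 and 30 minutes. Those times govern the second injection and discontinuation. Section 6.1.7 speaks of numbness within 15 minutes, Section 7.1.1 records the time to adequate anesthesia, and no section limits the checks to two times.

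**Conclusion.** The point holds for the cold-response duration. On the visible text it is either lip-numbness time plus a constant or a post-lidocaine time, and it has no meaning for a tooth that was cold-negative before injection. That conclusion follows from the schedule and needs no numerical assumption. The sizes (4.5% of trials flagging a true 4-minute onset difference, 44% flagging unequal block failure) depend on the assumed distributions and show the direction and possible extent of the error only.

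Two measures survive. Time to lip numbness remains usable for soft-tissue onset. The first cold test remains a valid yes/no check of the block in teeth that responded to cold at baseline. The change is worth making because the objective exists to address a stated controversy.

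**What to change.** In Sections 4.1.3 and 10.2.5, and in the matching Protocol Summary entries:

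1. Remove the time to a negative cold response as an onset endpoint. Keep time to lip numbness, labeled as soft-tissue onset, and reword Section 3.3 so that it does not promise an estimate of pulpal onset.
2. Carry the statement in Section 2.2.2 through to the endpoint and analysis. IANB success is a negative response at the first cold test, before any lidocaine supplement, among teeth cold-positive at baseline. Compare it with the Fisher's exact test already planned for success. Report the post-lidocaine test separately, as a result of the combined regimen.

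If Figure 1 or the method form does contain a cold retest before lidocaine, say so in the text and reconsider item 1.

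The cost is the loss of one exploratory endpoint and a smaller denominator for the cold-test analysis. The documents give no expected share of cold-negative teeth, so the size of that loss cannot be stated. Injections, the test sequence and data collection do not change.

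### The number of supplemental injections is listed as an ordered exploratory endpoint, but the only test that covers it is Fisher's exact test of anesthetic success, so its order goes unused

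*Combined protocol and SAP*

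**What the plan says.** Section 4.1.3 lists "Number of supplemental injections" as an endpoint separate from the binary cold-test result. Section 10.2.5 then merges the two: "The success of LLA will be determined by the cold test results (+/-) and the number of supplemental injections". The single test named for success is given as "For comparison of success of LLA between the 2 arms we will use Fisher's exact test"; the Statistical Analysis entry of the Protocol Summary says the same. The rank test is reserved for the two onset times: "For comparison of onset of LLA between the 2 arms we will use a Wilcoxon Rank Sum test". The level comes from Section 10.2.2: "All analyses will be done with significance level of 5% (2-sided) unless specified otherwise".

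Three other provisions bear on the count:

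- It is capped, because Section 6.1.7 states "Subjects who need supplemental injections more than 2 times will be excluded from the study".
- Its starting value is unclear, because Section 2.2.2 states "A supplemental buccal infiltration and intraligamentary (IL) injection will be given with Lidocaine HCl 2% 1:100000 to all patients".
- Section 10.2.1 nevertheless states "All analyses will be intent-to-treat dataset that includes all randomized patients and will use the analysis dataset", and Section 5.8.2 says that anesthetic failures will be recorded and analyzed to compare the two agents.

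**The concern.** A count that runs from little further anesthesia, to more, to failure is ordered. Section 10.2.5 leaves two ways to apply Fisher's test to it. One is to cut the count into success and failure, which merges levels; no cut-off is stated. The other is to test the unordered table of counts against arm, which treats the levels as interchangeable labels. Either way, the listed endpoint has no comparison on its own scale.

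At stake is how well the trial can speak to a question it raises itself. Sections 2.1 and 2.3 describe the anesthetic success of bupivacaine as controversial, and Section 3 gives that as the reason for the exploratory objective. A general tendency toward more supplemental anesthesia in one arm is the pattern a rank test is built to detect.

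**Working it through.** **The plan's own figures.** None exists for this endpoint: no distribution, effect size or power target. The only power statement concerns the primary OHIP-14 comparison (40 per arm, difference 9.3, SD 13.3, two-sided 2.5%). It reproduces: t-test power is 79.8%, and 80/(1 − 0.2) = 100 enrolled. Here it serves only to fix the arm sizes, 40 evaluable and 50 enrolled.

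**Inputs.** From the documents: 1:1 allocation, 40 or 50 per arm, two-sided 5%. Assumed: three ordered levels with more than 2 times as the top level; lidocaine distributions of 70/20/10%, 50/35/15% and 80/15/5%; and a proportional-odds shift with odds ratio (OR) 2 to 3 toward more injections with bupivacaine.

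**Bupivacaine distribution.** For each cumulative probability C under lidocaine, the bupivacaine odds are [C/(1 − C)]/OR. For 70/20/10% and OR 2.5:

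- 0.70/0.30 = 2.333; 2.333/2.5 = 0.933; 0.933/1.933 = 48.3%
- 0.90/0.10 = 9; 9/2.5 = 3.6; 3.6/4.6 = 78.3%
- Levels: 48.3%, 30.0% (78.3 − 48.3) and 21.7% (100 − 78.3)

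**Tests compared by simulation.** The Wilcoxon statistic is the midrank sum, with tie-corrected variance (n²/12)[(2n + 1) − Σ(t³ − t)/(2n(2n − 1))], where t is the number of subjects at each level. Fisher's test is applied at the better of the two cuts. An uncorrected chi-square test at the same cut separates two sources of loss: Wilcoxon minus chi-square is the cost of ignoring order, and chi-square minus Fisher is the cost of Fisher's conservatism.

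Power (%) with 50 per arm, at OR 2 / 2.5 / 3:

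| Lidocaine | Wilcoxon | Chi-square | Fisher | Total gap | Of which order | Of which conservatism |
|---|---|---|---|---|---|---|
| 70/20/10 | 41/63/79 | 40/61/78 | 32/53/71 | 9/10/8 | 1/2/1 | 8/8/7 |
| 50/35/15 | 46/67/84 | 41/60/76 | 32/53/69 | 14/14/15 | 5/7/8 | 9/7/7 |
| 80/15/5 | 33/53/71 | 33/53/69 | 25/45/63 | 8/8/8 | 0/0/2 | 8/8/6 |

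Type I error was about 4 to 5% for Wilcoxon, 4.4 to 5.3% for chi-square and 2.3 to 3.1% for Fisher. With 40 per arm the total gap is about 7 to 18 points. Across 40 and 50 per arm, the order component stays at about 0 to 2 points for the first and third distributions and is about 3 to 10 for the second.

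**Other readings of the plan.**

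- *Cut at more than 2 times* (50 per arm, OR 2.5): Fisher's power is roughly 10 to 38%, against 53 to 69% for Wilcoxon. This cut merges most of the information.
- *Unordered 2×3 Fisher table* (50 per arm, OR 2 to 3): Wilcoxon gains about 8 to 12 points. Conservatism explains less here, since that test's type I error was 4.3 to 4.6% in the null cases run.
- *Only two values*: if the routine infiltration and intraligamentary set counts as the first time and excluded subjects are dropped, only 1 and 2 remain. There is then no order to lose. A gap of 7 to 9 points persists, all of it from conservatism.

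**Differences that are not a consistent shift** (40 per arm, unordered Fisher table):

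- 50/30/20% against 30/50/20%: Fisher 40%, Wilcoxon 27%
- 50/40/10% against 40/25/35%: Fisher 68%, Wilcoxon 42%

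The advantage reverses in both.

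**The case against.** The strongest reply is that the plan never says Fisher's test is applied to the count. Success may be meant as a yes/no outcome, for which Fisher's test is valid. The protocol does treat failure as binary elsewhere, in the exclusion rule and in the stopping rule of Section 10.2.6. This stands in part: Fisher's test is not an error, and the missing cut-off and combining rule for success is a gap of its own. It does not remove the point, because a binary success outcome leaves the separately listed count with no analysis on its own scale.

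A reader might also infer that discarding the order is what costs the whole 7 to 18 points. The figures do not support that. At the best cut, an ordinary chi-square test, which also ignores order, recovers most of the gap in two of the three assumed distributions and roughly half in the other. Nor do the documents supply any distribution from which a loss could be stated as fact, and the proportional-odds assumption itself favors Wilcoxon.

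Finally, the objective is exploratory and has no power target. Section 3.3 asks whether success is not different between agents, and a more powerful test of difference does not establish that. This limits the importance of the point, not its correctness.

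**Conclusion.** The point holds as a low-priority improvement. The endpoint is ordered, the only named test that covers it does not use the order, and a suitable test already stands in the same section.

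The size is conditional on three levels with failures ranked highest, one of three assumed distributions, and a consistent shift. The part due to ignoring order is small when the cut is well placed and larger when it falls at more than 2 times. The number of levels is itself uncertain, because the documents do not settle whether the routine set counts. It would be wrong to conclude that Fisher's test is invalid here, that Wilcoxon is always the stronger test, or that the primary or secondary analyses are affected.

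**What to change.** In Section 10.2.5 and the synopsis:

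1. Keep Fisher's exact test for the binary cold-test result.
2. Compare the number of supplemental injections between arms as an ordered variable, with a tie-corrected Wilcoxon rank sum test.
3. State whether the routine infiltration plus intraligamentary set is counted, and whether the unit is injections (as in Sections 4.1.3 and 5.3) or times (as in Sections 2.2.2, 5.8.1 and 6.1.7).
4. Give the highest rank to randomized subjects excluded for needing more than 2 supplemental times. Do the same for those excluded for failed lip numbness after two nerve blocks, who leave before any count can arise, or report that group separately by arm.
5. Report the full distribution by arm, so that patterns other than a shift can be seen.

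The cost is a few sentences of wording. Sections 6.1.9 and 7.1.1 already provide for recording supplemental anesthesia, so no new data or subjects are needed. The small downside is one more exploratory test, with less power for non-monotone differences.
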